8.2 Responsibility for Analyses/In-House Blinding

The statistical analysis of the data obtained from this study will be the responsibility of the Clinical Biostatistics department of the SPONSOR.

This study will be conducted as a double-blind study under in-house blinding procedures. The official, final database will not be unblinded until medical/scientific review has been performed, protocol deviations have been identified, and data have been declared final and complete.

The Clinical Biostatistics department will generate the randomized allocation schedule(s) for study treatment assignment. Randomization will be implemented in an interactive voice response system (IVRS).

This study that will be conducted in 2 stages which will enroll an adult cohort (Stage 1) and an infant cohort (Stage 2). Additionally, the infant cohort will be enrolled in 2 parts (I and II) in order to evaluate safety in a smaller group of infants prior to full enrollment of Stage 2. Prior to proceeding between Stage 1 and 2, as well as between Stage 2 part I and Stage 2 part II, the safety and tolerability of V114 will be carefully evaluated by the eDMC. For this Phase I-II study, an internal statistician and statistical programmer assigned to the protocol will be unblinded throughout the duration of the study to facilitate the interim reviews of the safety data by the eDMC. All other MRL employees directly involved with the conduct of this trial will remain blinded to the subject's treatment assignment until medical/scientific review of all safety and immunogenicity data has been performed, protocol deviations have been identified, and data have been declared final and complete.

The 2 planned interim analyses are described in Section 8.7. The results of each interim analysis will not be shared with the investigators prior to the completion of the study. Subject-level unblinding will be restricted to an internal unblinded statistician and an unblinded statistical programmer performing the interim analysis.

Results of the interim analyses will be provided by the unblinded statistician to the eDMC. Group summaries will be reviewed by the Sponsor's study team in order to make scientific decisions for future studies.

8.3 Hypotheses/Estimation

Objectives of the study are stated in Section 3.0. This is an estimation study and no formal hypothesis testing will be performed.

8.4 Analysis Endpoints

Immunogenicity and safety endpoints that will be evaluated for within- and between-treatment differences are listed below.

8.4.1 Immunogenicity Endpoints

Adult Stage

For the adult stage of the study, there are no primary immunogenicity endpoints. The secondary immunogenicity endpoints are the serotype-specific IgG GMCs and fold-rises from baseline as measured in the Pn ECL assay at 1 month postvaccination for the 15 serotypes in V114.

Infant Stage

For the infant stage of the study, the primary immunogenicity endpoints are the serotype-specific IgG GMCs as measured in the Pn ECL assay at 1 month PD3 for the 15 serotypes in V114 and 13 serotypes in Prevnar 13TM.

The secondary immunogenicity endpoints include (1) the proportion of subjects achieving IgG concentrations $\geq 0.35\mu\text{g/mL}$ at 1 month PD3, pre-dose 4, and 1 month PD4, and (2) the GMCs at pre-dose 4 and 1 month PD4 for the 15 serotypes in V114 and 13 serotypes in Prevnar 13TM.

The exploratory immunogenicity endpoints include the proportion of subjects with OPA titer ≥ 8 and OPA GMTs at 1 month PD3, pre-dose 4, and 1 month PD4 for the 15 serotypes in V114 and 13 serotypes in Prevnar 13TM.

8.4.2 Safety Endpoints

Refer to Section 4.2.3.2 for the description of the safety measures in this study.

Safety and tolerability will be assessed by clinical review of all relevant parameters including AEs, within both the adult and infant cohorts. Tier 1 events for this study will consist of the solicited injection-site and solicited systemic AEs in the infant cohort.

8.5 Analysis Populations

8.5.1 Immunogenicity Analysis Populations

The primary immunogenicity analysis population will be the PP population. The PP population consists of those subjects who are not considered protocol violators. For the adult cohort, the violations include, but are not limited to: failure to receive the scheduled dose of correct clinical material, and lack of valid serology results available from 30 to 44 days following dose 1. For the infant cohort, the violations include, but are not limited to: failure to receive the scheduled doses (at least 28 days between doses 1 and 2 and between doses 2 and 3, and dose 4 at 12 months to 15 months of age) of correct clinical material, and lack of valid serology results available from 28 to 42 days following dose 3 or dose 4. The final determination on protocol violators will be made prior to unblinding of the database and will be documented in a separate memo.

The Full Analysis Set (FAS) population will also be used for supplementary analysis of the primary analyses. The FAS population consists of all randomized subjects who received at least one vaccination and have at least one serology result. Subjects will be included in the treatment group to which they are randomized for the analysis of immunogenicity data.

Details on the approach to handling missing data are provided in Section [8.6](#) Statistical Methods.

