4.3 Benefit/Risk

A subset of subjects will receive Prevnar 13™ which is the standard of care and is serving as the active comparator in this study. V114 is aimed at providing comparable immune responses to Prevnar 13™ for the shared serotypes while providing additional coverage for the 2 serotypes (22F and 33F) unique to V114. It is unknown if the investigational V114 will have the same benefit as Prevnar 13™. As a possible rescue medication in this study, subjects who fail to achieve adequate immune responses to serotype 19A (individually) and/or to 4 or more serotypes in common between Prevnar 13™ and V114 following the

third dose of study vaccine will be offered an additional dose of licensed pneumococcal conjugate vaccine between 9 and 12 months of age. (See section 5.6 Rescue Medications & Supportive Care for additional details).

Additional details regarding specific benefits and risks for subjects participating in this clinical trial may be found in the accompanying Investigators Brochure (IB) and Informed Consent documents.

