5.6 Rescue Medications & Supportive Care

Infant subjects who fail to achieve adequate serologic responses following the third dose of study vaccine will be offered an additional dose of licensed pneumococcal conjugate vaccine outside of this protocol. Any study subject with serotype-specific pneumococcal IgG (as measured by Pn ECL assay) below 0.35 μ g/mL for serotype 19A (individually) and/or 4 or more serotypes in common between V114 and Prevnar 13TM at 1 month PD3, will be given one dose of licensed pneumococcal conjugate vaccine as soon as possible after serological results are available. All subjects who meet the rescue criterion must be discontinued from the study prior to administering the additional dose of licensed pneumococcal conjugate vaccine. The discontinuation date should be the date the parent/legal guardian was notified of the child's meeting the rescue criterion. Adverse events or changes to medical history occurring after the 14 days of safety follow up for Dose 3 and the discontinuation should be reported in the database; no additional immunogenicity blood sample should be drawn. If an SAE occurs between the 14 days of safety follow up for Dose 3 and the discontinuation, that event must be reported. The serologic threshold value of 0.35 μ g/mL was recommended by a WHO expert panel as an acceptable threshold value for evaluating the clinical performance of pneumococcal conjugate vaccines in infants [3],[4]. Adequate treatment provisions,

including epinephrine, should be available for immediate use should an anaphylactic or anaphylactoid reaction occur.

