5.8 Subject Withdrawal/Discontinuation Criteria

Subjects may withdraw consent at any time for any reason or be dropped from the trial at the discretion of the investigator should any untoward effect occur. In addition, a subject may be withdrawn by the investigator or the Sponsor if enrollment into the trial is inappropriate, the trial plan is violated, or for administrative and/or other safety reasons. Specific details regarding discontinuation or withdrawal procedures; including specific details regarding withdrawal from Future Biomedical Research, are provided in Section 7.1.4 – Other Procedures.

In this trial, a subject may discontinue from vaccination but continue to participate in the regularly scheduled activities, as long as the subject does not withdraw consent. Discontinuation from vaccination is permanent. Once a subject has discontinued vaccination, even though he/she continues to be monitored in the trial, he/she shall not be allowed to begin vaccination again.

A subject must be discontinued from the trial for any of the following reasons:

- The subject or legal representative (such as a parent or legal guardian) withdraws consent.
- The subject has a medical condition or personal circumstance which, in the opinion of the investigator and/or SPONSOR, places the subject at unnecessary risk through continued participation in the trial or does not allow the subject to adhere to the requirements of the protocol.
- In stage 2 (Parts I and II), any infant subject that fails to achieve adequate serologic responses, as described in Section 5.6, will be discontinued from the study.

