Visit Timing:	Age:~2 months DOSE 1	Age:~4 months DOSE 2	Age:~6 months DOSE 3	30 days after Visit 3	Age:~12 to 15 months DOSE 4	30 days after Visit 5
Visit Window:	≥42 days of age to ≤90 days of age	4 months of age to 1 day prior to 5 months of age	6 months of age to 1 day prior to 7 months of age	28 to 42 days PD3	12 months of age to 1 day prior to 16 months of age	28 to 42 days PD4
Administrative Procedures						
Informed Consent ^b	X					
Informed Consent for Future Biomedical Research (FBR) ^c	X					
Inclusion/Exclusion Criteria	X					
Subject Identification Card	X					
Medical History	X					
Update Medical History (New condition not already recorded as medical history or adverse experiences)		X	X	X	X	X
Concomitant Medication Review	X	X	X	X	X	X
Vaccination Allocation/Randomization	X					
Study Vaccine Administration ^d	X	X	X		X	
Childhood Vaccines ^e	X	X	X		X	
Provide Electronic Vaccination Report Card (VRC)	X					
Review VRC data ^f		X	X	X		X
Clinical Procedures/Assessments						
Full Physical Examination	X					
Targeted Physical Examination		X	X		X	
Obtain Rectal Temperature ^g	X	X	X		X	
30 Minutes Postvaccination Observation Period	X	X	X		X	
Adverse Experience Monitoring ^h	X	X	X	X	X	X
Assess for Serious Adverse Experiences ⁱ	X	X	X	X	X	X
Laboratory Procedures/Assessments						
Collect blood samples for immunogenicity assays (4-5 mL) ^{h, i}				X	X	X
Collect Buccal Swabs for Future Biomedical Research ^c	X					

Infant Cohort						
Visit Number:	1 ^a	2 ^a	3	4	5	6
Visit Timing:	Age:~2 months DOSE 1	Age:~4 months DOSE 2	Age:~6 months DOSE 3	30 days after Visit 3	Age:~12 to 15 months DOSE 4	30 days after Visit 5
Visit Window:	≥42 days of age to ≤90 days of age	4 months of age to 1 day prior to 5 months of age	6 months of age to 1 day prior to 7 months of age	28 to 42 days PD3	12 months of age to 1 day prior to 16 months of age	28 to 42 days PD4

a. For Visits 1 and 2, study coordinator should review the electronic Vaccination Report Card (VRC) in the vendors database at 14 days postvaccination (0 to plus 5 day window) and call the parent/legal guardian if there is a need to address questions (document phone call in study chart). The site will review VRC with parent/legal guardian at next visit.

b. Consent must be obtained prior to any study procedures.

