Endpoint/Variable (Description, Time Point)	Statistical Method	Analysis Population	Missing Data Approach
Primary Objectives			
PD3 GMCs, for the 15 serotypes in V114 and the 13 serotypes in Prevnar 13™ [V114 medium, V114 high, Prevnar 13™] (Infant Primary Objective #2)	
 • Within-group GMCs and 95% CI • GMC ratio (V114 arm/Prevnar 13™) and 95% CI (2-sample t-test) for common serotypes 	Infant Per-Protocol	Missing data will be dropped
PD3 GMCs, for the 15 serotypes in V114 and the 13 serotypes in Prevnar 13™ [V114 medium, V114 high, Prevnar 13™] (Infant Primary Objective #2)	
 • Within-group GMCs and 95% CI • GMC ratio (V114 arm/Prevnar 13™) and 95% CI (2-sample t-test) for common serotypes 	Infant FAS [Supportive]	Missing data will be dropped
Secondary Objectives			
PD3, pre-dose 4, PD4 % \geq 0.35, for the 15 serotypes in V114 and the 13 serotypes in Prevnar 13™ [V114 medium, V114 high, Prevnar 13™] (Infant Secondary Objective #1)	
 • Within-group %\geq0.35 and 95% CI • Difference in %\geq0.35 (V114 arm-Prevnar 13™) and 95% CI (M&N) for common serotypes 	Infant Per-Protocol	Missing data will be dropped
Pre-dose 4 and PD4 GMCs, for the 15 serotypes in V114 and the 13 serotypes in Prevnar 13™ [V114 medium, V114 high, Prevnar 13™] (Infant Secondary Objective #2)	
 • Within-group GMCs and 95% CI • GMC ratio (V114 arm/Prevnar 13™) and 95% CI (2-sample t-test) for common serotypes 	Infant Per-Protocol	Missing data will be dropped
PD1 GMCs and fold-rises from baseline, for 15 serotypes in V114 and the 13 serotypes in Prevnar 13™ [V114 medium, V114 high] (Adult Secondary Objective #1)	
 • Within-group GMCs and 95% CI • Within-group fold-rises from baseline and 95% CI 	Adult Per-Protocol	Missing data will be dropped

The strategy to address multiplicity issues is described in Section 8.7, Interim Analyses and in Section 8.8, Multiplicity.

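### The infant per-protocol definition requires dose 4, but infants with low PD3 antibody must be discontinued, so the PD3 analysis set may be selected on the PD3 result

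*Combined protocol and SAP*

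**What the plan says.** Section 8.5.1 makes PP the primary immunogenicity population and defines it once for infants. The listed violations are failure to receive the scheduled doses and lack of valid serology. The dose requirement covers the spacing of doses 1 to 3 and then adds "and dose 4 at 12 months to 15 months of age) of correct clinical material, and lack of valid serology results available" within 28 to 42 days of dose 3 or dose 4. No separate PD3 or PD4 set is named.

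In Table 4 (Section 8.6.1) the population for the primary PD3 GMCs and ratios, and for the secondary PD3 response rates (share at or above 0.35 µg/mL), is "Infant Per-Protocol". A supportive FAS row exists only for the PD3 GMCs, and Section 8.5.1 likewise limits FAS to the primary analyses.

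Section 5.6 sets the rescue criterion as PD3 IgG below 0.35 µg/mL for 19A alone and/or for 4 or more common serotypes, and states: "All subjects who meet the rescue criterion must be discontinued from the study prior to administering the additional dose". Section 5.8 repeats it: "any infant subject that fails to achieve adequate serologic responses, as described in Section 5.6, will be discontinued from the study". On timing, Section 5.6 says "as soon as possible after serological results are available", and Section 4.3 says such infants "will be offered an additional dose of licensed pneumococcal conjugate vaccine between 9 and 12 months of age". The dose 4 window in the flow chart (Section 6.0) is "12 months of age to 1 day prior to 16 months of age".

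**The concern.** An infant discontinued under Section 5.6 before dose 4 cannot receive dose 4. Under the PP definition as written, that infant has a listed violation and leaves the PP set, and so leaves the PD3 analysis as well. Membership of the PD3 set would then depend on the PD3 outcome.

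For 19A, the value that triggers removal (0.35) is also the value that defines the response-rate endpoint, so the rate would be 100% in every arm by construction. The 19A GMCs would be biased upward. The V114/Prevnar 13 ratios could be biased in either direction, depending on how the two distributions differ.

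Section 8.3 calls this an estimation study, so these estimates are its main product. Section 4.2.1 says its purpose is to optimise the formulation for serotypes with suboptimal responses, and the infants at risk of removal are the low responders.

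**Working it through.** **Plan's own figure.** Section 8.9 states 94.7% power for a 2-fold lower GMC (SD of ln IgG 1.0, 45 per arm, one-sided 0.05). The noncentrality is ln 2 / (1.0 × √(2/45)) = 0.693/0.211 = 3.29. With 88 df the noncentral t gives 94.7%, so the figure reproduces. It assumes 45 infants per arm evaluable at PD3, not selected on their PD3 value.

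**Timing** (month = 30.44 days). The PD3 sample falls between 6 months + 28 days (day 210.6) and 7 months - 1 day + 42 days (day 254.1). The earliest dose 4 is at 12 months (day 365.3). The gap is therefore 155 down to 111 days. No assay turnaround is given.

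**Removal and GMC inflation, 19A trigger only.** The documents give no 19A GMC or SD, so the Table 8 grid is assumed (GMC 1 to 3, SD 0.8 to 1.4). With ln IgG normal:

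- z = ln(0.35/GMC)/SD
- share removed r = Φ(z)
- GMC inflation = exp(SD × φ(z)/(1 - Φ(z)))

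| GMC | SD | z | Removed | Inflation |
|---|---|---|---|---|
| 1 | 1.0 | -1.050 | 14.7% | ×1.309 |
| 2 | 1.0 | -1.743 | 4.1% | ×1.095 |
| 3 | 0.8 | -2.686 | 0.4% | ×1.009 (smallest) |
| 1 | 1.4 | -0.750 | 22.7% | ×1.725 (largest) |

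For GMC 1 vs 2 at SD 1.0, the ratio becomes 0.50 × 1.309/1.095 = 0.60.

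**Ratio and CI coverage.** 40,000 simulated trials per case, 45 per arm before removal, pooled two-sample t on ln IgG. Coverage without removal was 95% throughout.

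| V114 GMC (SD) vs Prevnar 13 GMC (SD) | True ratio | Ratio after removal | Coverage of true ratio |
|---|---|---|---|
| 2 (1.0) vs 2 (1.0) | 1.00 | 1.00 | 95% |
| 2 (0.8) vs 3 (0.8) | 0.67 | 0.68 | 95% |
| 2 (1.0) vs 3 (1.0) | 0.67 | 0.70 | 94% |
| 1 (1.0) vs 2 (1.0) | 0.50 | 0.60 | 85% |
| 2 (1.0) vs 3 (1.2) | 0.67 | 0.66 | 95% |
| 2 (1.2) vs 3 (1.0) | 0.67 | 0.77 | about 90% |
| 1.5 (0.8) vs 2 (1.4) | 0.75 | 0.60 | 82% |
| 2 (0.8) vs 2 (1.4) | 1.00 | 0.77 | 78% |
| 1.5 (1.4) vs 2 (0.8) | 0.75 | 1.07 | 62% |

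**19A response rate, GMC 1 vs 2, SD 1.0.** The true rates are 85.3% vs 95.9%, a difference of -10.6 points. With 45 per arm that is about 38/45 vs 43/45, or -11.1 points (Miettinen-Nurminen 95% CI -25.2 to +1.6). After removal it is 38/38 vs 43/43, a difference of 0 (-9.3 to +8.3).

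**Late results, same case.** If a share *a* of 19A failures is discontinued before dose 4, the expected PP rate is (1 - r)/(1 - r × a).

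| *a* | Rate difference (points) | GMC ratio |
|---|---|---|
| 100% | 0 | 0.60 |
| 90% | -1.3 | 0.59 |
| 75% | -3.1 | 0.57 |
| 50% | -5.9 | 0.54 |
| 25% | -8.4 | 0.52 |

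**Full rescue rule.** Simulating all 13 common serotypes (SD 1.0, assumed correlation 0 to 0.6) removes 22% to 26% of infants at GMC 1.0 and 4% to 6.5% at GMC 2.0. The GMC of another common serotype rises from 1.0 to 1.04-1.36, or from 2.0 to 2.00-2.21.

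**The case against.** The best reply is that a time-point set is what the authors meant. The serology clause accepts a sample after dose 3 or dose 4. Section 8.9 ties evaluability to PD3 alone. The second interim (Section 8.7) is triggered by PD3 results, when infants under 12 months are not yet due for dose 4. An infant discontinued because the protocol requires it has also broken no rule, and dose 4 is arguably no longer scheduled for that infant. The violation list is expressly not exhaustive, and the violator memo is settled before the database is unblinded.

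There are also safeguards. FAS keeps these infants for the PD3 GMCs. Section 8.6.1 promises reverse cumulative distribution displays of PD3 IgG. Section 8.6.3 displays reasons for discontinuation. A 19A rate of exactly 100% in every arm would be noticed. Finally, the largest ratio distortions above need SDs of 0.8 and 1.4 in the two arms, whereas Table 7 uses one SD per comparison.

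Much of this stands. The time-point reading is plausible, the large-SD-gap cases are extremes, and for several common-SD cases the ratio bias is negligible. But no sentence limits dose 4 to the PD4 analyses or exempts protocol-required discontinuations. The dose 3 or dose 4 alternative attaches only to serology. The memo decides case by case what the definition should say, and the interim and final PD3 sets could differ. The distribution displays have no stated population. FAS does not reach response rates, the endpoint most affected.

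**Conclusion.** The concern holds as an unresolved ambiguity in the PP definition, not as a demonstrated bias. Under a time-point reading there is no problem. Under the definition as written, the PD3 set is selected on the PD3 result.

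In that case the 19A response-rate difference is erased if results are acted on before dose 4, and shrunk if some arrive late. The 19A GMC is inflated by 0.9% to 72.5% over the plan's own grid. The GMC ratio is unbiased when the arms have the same distribution. It is pulled toward 1 when the SD is shared and V114 is lower, and can move away from 1 or past it when SDs differ.

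These sizes assume normal ln IgG, GMC 1 to 3 and SD 0.8 to 1.4. Apart from the full-rule simulation, they count only the 19A trigger. Ordinary drop-out after PD3 is not counted. Because the rule touches a primary and a secondary PD3 analysis and is cheap to settle, it should be fixed.

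**What to change.** - In Section 8.5.1 and Table 4, define PP by time point. PD3 PP should need only doses 1 to 3 and a valid PD3 sample at 28 to 42 days, and should keep infants later discontinued under Section 5.6. Apply the dose 4 requirement to PD4 analyses only, and state what the pre-dose 4 analysis requires.
- Add an FAS row for PD3 response rates in Table 4.
- Report Section 5.6 discontinuations by arm as their own category within the Section 8.6.3 display.
- Settle the PD3 violator list before the second interim analysis, so that the interim and the final report use the same PD3 set.

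The cost is a few sentences, one table row, one reporting category and an earlier memo. No extra subjects, visits or samples are needed, and the rescue and discontinuation rules are left as they are.

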8.5.2 Safety Analysis Populations

The All Subjects as Treated (ASaT) population will be used for the analysis of safety data in this study. The ASaT population consists of all randomized subjects who received at least one dose of study treatment. Subjects will be included in the treatment group corresponding to the study treatment they actually received for the analysis of safety data using the ASaT population. For most subjects this will be the treatment group to which they are randomized. Subjects who take incorrect study treatment for the entire treatment period will be included in the treatment group corresponding to the study treatment actually received.

Details on the approach to handling missing data for safety analyses are provided in Section [8.6](#) Statistical Methods.

8.6 Statistical Methods

8.6.1 Statistical Methods for Efficacy Analyses

This section describes the statistical methods that address the primary and secondary objectives. Methods related to exploratory objectives will be described in the supplemental SAP.

Analysis of the immunogenicity data from the infant stage of the study will be based on the combined data from Stage 2 Part I and Stage 2 Part II.

To address the primary infant immunogenicity objective #2, GMCs at 1 month PD3 along with two-sided 95% CIs will be computed for the 15 serotypes in V114 for V114 medium, V114 high, and 13 serotypes in Prevnar 13TM. Point estimates of GMCs are the exponentiated estimates of the mean log_e concentrations. The confidence intervals for GMCs are the exponentiated confidence intervals for the mean log_e concentrations, based on 1-sample t-distributions. Additionally, GMC ratios (V114/Prevnar 13TM) along with two-sided 95% CIs will be computed for each of V114 medium and V114 high relative to Prevnar 13TM for the 13 common serotypes. The CI for the ratio will be calculated using a 2-sample t-test approach based on the natural logarithm of the ratio.

To address the secondary infant immunogenicity objective #1, the proportion of subjects achieving the serotype-specific threshold value of $\geq 0.35\mu\text{g}/\text{mL}$ for the 15 serotypes at 1 month PD3 along with the 95% CI will be calculated for V114 medium, V114 high, and the 13 serotypes in Prevnar 13TM. The one-sample two-sided CIs will be computed using the exact CI method for a single binomial proportion given in Collett [7]. Additionally, the

difference (V114 minus Prevnar 13TM) in the proportion of subjects achieving an IgG concentration $\geq 0.35\mu\text{g/mL}$ along with two-sided 95% CIs will be computed for each of V114 medium and V114 high relative to Prevnar 13TM for the 13 serotypes in common. The CI for the difference will be computed using the method of Miettinen and Nurminen [8].

The additional secondary infant immunogenicity objective (#2) as well as the secondary adult immunogenicity objective #1 will utilize similar statistical methods as those outlined above.

Reverse cumulative distribution functions for both IgG and OPA levels at PD3 and PD4 will be graphically displayed by serotype in the CSR.

Table 4 summarizes the key immunogenicity analyses.

Table 4 Analysis Strategy for Key Immunogenicity Variables

Endpoint/Variable (Description, Time Point)	Statistical Method	Analysis Population	Missing Data Approach
Primary Objectives			
PD3 GMCs, for the 15 serotypes in V114 and the 13 serotypes in Prevnar 13™ [V114 medium, V114 high, Prevnar 13™] (Infant Primary Objective #2)	
 • Within-group GMCs and 95% CI • GMC ratio (V114 arm/Prevnar 13™) and 95% CI (2-sample t-test) for common serotypes 	Infant Per-Protocol	Missing data will be dropped
PD3 GMCs, for the 15 serotypes in V114 and the 13 serotypes in Prevnar 13™ [V114 medium, V114 high, Prevnar 13™] (Infant Primary Objective #2)	
 • Within-group GMCs and 95% CI • GMC ratio (V114 arm/Prevnar 13™) and 95% CI (2-sample t-test) for common serotypes 	Infant FAS [Supportive]	Missing data will be dropped
Secondary Objectives			
PD3, pre-dose 4, PD4 % \geq 0.35, for the 15 serotypes in V114 and the 13 serotypes in Prevnar 13™ [V114 medium, V114 high, Prevnar 13™] (Infant Secondary Objective #1)	
 • Within-group %\geq0.35 and 95% CI • Difference in %\geq0.35 (V114 arm-Prevnar 13™) and 95% CI (M&N) for common serotypes 	Infant Per-Protocol	Missing data will be dropped
Pre-dose 4 and PD4 GMCs, for the 15 serotypes in V114 and the 13 serotypes in Prevnar 13™ [V114 medium, V114 high, Prevnar 13™] (Infant Secondary Objective #2)	
 • Within-group GMCs and 95% CI • GMC ratio (V114 arm/Prevnar 13™) and 95% CI (2-sample t-test) for common serotypes 	Infant Per-Protocol	Missing data will be dropped
PD1 GMCs and fold-rises from baseline, for 15 serotypes in V114 and the 13 serotypes in Prevnar 13™ [V114 medium, V114 high] (Adult Secondary Objective #1)	
 • Within-group GMCs and 95% CI • Within-group fold-rises from baseline and 95% CI 	Adult Per-Protocol	Missing data will be dropped

The strategy to address multiplicity issues is described in Section 8.7, Interim Analyses and in Section 8.8, Multiplicity.

